### 10.4.5 Final Analysis

An interim analysis will not be performed. The final analysis of all endpoints will be performed at the end of the study.

### 11 Data Management

### 11.1.1 Data Collection

Data should be recorded on the appropriate Case Report Form (CRF) for all study subjects from whom informed consent is obtained, and no study treatment should be administered without written informed consent. CRFs will be retrieved by the study monitor during the monitoring visits and subsequently sent to the data manager. Incoming data will be reviewed to identify inconsistent and/or missing data. Data problems will be addressed by written queries to the site.

Version 6.0 Page 31 of 47

### 11.1.2 Case Report Forms

Standardized CRFs will be provided by the Sponsor to the site. The investigator is responsible for completion of the CRFs in a timely manner and should be up to date with the documentation before each monitoring visit.

### 11.1.3 Data Entry and Management

All original CRFs will be retrieved from the site by the study monitor and sent to the data management. Double data entry and computer programmed error checks will be carried out by data management personnel. The investigator will be queried on issues concerning completeness and consistency.

All above mentioned tasks will be carried out according to Straumann Standard Operating Procedures, except for those tasks performed by Straumann contracted Contract Research Organizations (CRO), where the CRO procedures shall be used.

### 12 Regulatory and Ethical Requirements

### 12.1 Basic requirements

The principal investigator/co-investigator shall confirm the eligibility of the subject by the screening test and confirm the conformity to the inclusion/exclusion criteria at the subject enrolment.

Also, the principal investigator/co-investigator shall keep knowledge about the subject's health condition by retaining the communication path to the subject for the emergency during the follow-up period, etc. Also, he/she shall make an effort to collect and transfer the safety information relevant to the investigational device with the cooperation of the relevant peoples involved to this study. In case of the occurrence of the adverse event, the principal investigator/co-investigator shall provide an appropriate treatment to ensure the subject's safety.

A Sponsor shall collect and examine information that is necessary for properly conducting a clinical trial, with respect to matters concerning the quality, efficacy, and safety of the investigational device and provide the head of the medical institution with such information.

Whenever the Sponsor finds any of the items such as disease, injury or death suspected due to adverse device effect, infection due to the investigational device or other events relates to the effectiveness or safety of the investigational device, Sponsor shall promptly notify the principal investigator and the head of the medical institution thereof.

### 12.2 Informed Consent

Each subject will be informed by the investigator of the overall requirements/procedures of the study after explaining the purposes of the study, the nature of the planned treatment and alternative procedures. In addition, he/ she will explain any risks, possible complications and benefits of the proposed treatment. The Institutional Review Board (IRB) approved consent form will be provided by the Sponsor.

The informed consent form will be valid only after it is dated and bears the name and signature of the principal investigator/co-investigator and subject.

Version 6.0 Page 32 of 47

The principal investigator/co-investigator shall provide the copy of it after it is dated and bears the name signature of the principal investigator/co-investigator and subject.

The informed consent document is written in accordance with the "Declaration of Helsinki" (as adopted by the 18th World Medical Assembly, 1964, and as revised in Tokyo (1975), Venice (1983), Hong Kong (1989), South Africa (1996), Edinburgh (2000), Washington (2002), Tokyo (2004) and Seoul (2008).

When the principal investigator/co-investigator obtained any information that might influence the subject's intent to participate in the clinical trial, the principal investigator/co-investigator shall promptly give such information to the subject, document the communication of the information, and confirm whether the subject is willing to continue his or her participation in the clinical trial.

The principal investigator, in such cases as stipulated under the preceding paragraph, shall revise the explanatory documents without delay whenever it is deemed necessary.

When the explanatory documents are revised pursuant to the preceding paragraph, the principal investigator shall report the fact to the head of the medical institution and obtain the subject's consent to continue his or her participation in the clinical trial.

#### 12.3 Institutional Review Board / Ethics Committee

Prior to initiation of any study procedures, the protocol, sample of CRF, explanatory documents and informed consent form will be submitted to an IRB or Ethics Committee for review and approval from the viewpoint of ethical, scientific and medical appropriateness. In addition, any amendments to the protocol or informed consent must be reviewed and approved by the IRB or Ethics Committee. The Sponsor must receive a letter documenting the IRB / Ethics Committee approval at the clinical site prior to the initiation of the study.

The investigator is responsible for providing the appropriate reports to the IRB or Ethics Committee during the course of the clinical study.

### 12.4 Regulatory Compliance

This study will be performed in compliance with the Declaration of Helsinki, ISO 14155, this protocol and the relevant local regulations and laws.

### 13 Study Management

#### 13.1 Reports and Record Management

### 13.1.1 Investigator Records

The investigator will receive an investigator file with all required study documents, including the instructions for use, protocol, CRF, informed consent, study contract and confidentiality agreement, insurance certificate, IRB/ IEC approval, CV of investigator and various other documents. Prior to the initiation of the study the investigator has to provide several documents including a signed confidentiality agreement, the curriculum vitae of the investigator(s), a signed copy of the final protocol and any amendments, a signed copy of the clinical study agreement with the Sponsor and various other documents on request.

Version 6.0 Page 33 of 47

### 13.1.2 Case Report Forms

The investigator shall supply the Sponsor on request with any required background data from the study documentation or any other clinical records. This is particularly important when errors in data transcription are suspected. The investigator will be responsible for the accuracy of the data entered in the case report form. All entries must be written in black or blue ink and all deletions, additions or changes must be initialled and dated (additional information sheet on how to fill out the CRF). The forms must be available for review/ collection to designated Straumann representatives at each scheduled monitoring visit. The investigator will also allow the Straumann representative and/ or regulatory bodies to review the data reported in the CRFs with the source documents as far as is permitted by local regulations and provided that the subject confidentiality is protected.

#### 13.1.3 Source Documents

Source documents are defined as the original point of entry of a specific data point. Source documents will include, but are not limited to, progress notes, electronic data, computer printouts, radiographs, and recorded data from automated instruments. Certain data recorded in the CRF can be considered as source data. In this study the following data recorded in the CRF can be considered as source data: Full Mouth Plaque Index (PI) according to O'Leary et al. 1972 and the Full Mouth Bleeding on Probing (BoP) Index according to Ainamo and Bay 1975. All source documents pertaining to this study will be maintained by the investigator and made available for inspection by authorized persons and for source data verification during monitoring visits. 100% of source data verification will be performed on critical variables. Besides of general information the investigator has to document each and every requested data point of the CRF/protocol first in his source data. The transcription of these source data into the CRF might be done later by the investigator or authorized designee.

### 13.1.4 Records/data Retention

Originals of the radiographs, casts, or other items and originals of the study records and clinical data forms will be maintained by the study monitor in the file established for this study. All study documentation (CRFs, Investigators files, subject x-rays and photographs) should be kept at the study site after the study is completed for at least 15 years following the completion of the study as determined by the Sponsor. The investigator should be available to answer any queries associated with the study during this time. If the investigator is no longer working at the site, he is obliged to inform Straumann who will be in charge of the archived documents and who is responsible to answer questions once he is not at the site. If the documents are moved to another location the investigator must inform Institut Straumann AG about the move. All other study records will be kept by Straumann once the study has been completed. These records will be maintained at Straumann according to Straumann standard operating procedures.

#### 13.1.5 Subject Data Protection

The name of the subject as well as all other personal data will be kept under the strict confidence by the investigator. If in case for medical reasons, it will be necessary during the course of the study to identify the subject this will be done under attention of the medical secrecy. The investigator will assure that all CRFs and other documents that will be handed out to Institute Straumann AG will not contain any personal subject data. The investigator will

Version 6.0 Page 34 of 47

prepare a separate list which will allow the identification of the subject. This list will contain subject numbers, initials, names and addresses of the subject and will be filed in the investigator's file.

During the regular monitoring visits, audits or inspections by the authorities, the subject cards will be inspected by authorised persons (e.g. monitors, auditors). These persons are committed legally on their secrecy.

### 13.2 Quality Control and Assurance

### 13.2.1 Monitoring (general aspects)

Straumann will assign a qualified individual to monitor the study. The general monitoring procedures for this study are described below. In general the monitor has to follow the applicable laws and guidelines during all monitoring activities.

The monitor will be responsible for determining and documenting that each investigator clearly understands and accepts the responsibilities and obligations of conducting a clinical study.

It is understood that the responsible Straumann monitor (or designee) will contact and visit the investigator regularly and will be allowed, on request, to inspect the various records of the trial including the CRFs and other pertinent data, provided that the subject confidentiality is maintained in accord with local requirements.

It will be the monitor's responsibility to inspect the CRFs at regular intervals throughout the study, to verify the adherence to the protocol and the completeness, consistency and accuracy of the data being entered on them. The monitor will need to have access to storage locations of study devices and study supplies, to treatment/examination rooms and rooms where any study related activity takes place, and to all records associated with the study as well as to all other original patient records/source documents to verify the entries on the CRF. The investigator (or his/her deputy) agrees to cooperate with the monitor to ensure that any problem detected in the course of these monitoring visits is resolved.

### 13.2.2 Pre-study Visit

The main purpose of the pre-study visit is to conduct a detailed discussion of the planned study, based on the draft protocol and eCRF/CRF (if available). If initially only a general outline exists and development of a study protocol largely depends on substantial input from the investigator, all relevant information has to be obtained in the pre-study phase to allow for the writing of the protocol and the designing of the eCRF/CRF.

#### 13.2.3 Study Initiation Visit

If the required documentation including the insurance certificate, the devices and all study supplies as well as the IEC approval and the approval of the authorities (if applicable) are on file/on site, the monitor is allowed to perform the study initiation visit. The investigator(s), co-investigator(s) and all persons to whom the investigator has delegated significant study-related duties should be present for the initiation visit. The investigator(s), co-investigator(s) or any other persons to whom the investigator has delegated significant study-related duties are not allowed to perform any subject related action before the study initiation visit.

Version 6.0 Page 35 of 47

The monitor will address issues regarding the performance of the study with focus on the responsibilities of the investigator and co-workers during the initiation visit in detail with all persons involved, if not previously discussed and documented.

### 13.2.4 Routine Monitoring Visits

Monitoring visits will be scheduled and conducted periodically.

- The protocol is being properly followed
- The IECs and authorities approved or has been notified of any protocol changes
- Informed consent has been obtained for each and every subject before any subject related activity
- Accurate, complete, and current records are being maintained, and the information recorded on the CRFs is representative of the subject's record and other source data (source document verification)
- Accurate, complete, and timely adverse event and serious adverse event reporting is followed
- The reason for a subject's withdrawal has been documented
- Reports are being submitted to the IEC, authorities and to the Sponsor
- The appropriate staff is carrying out the study activities
- · All logs are valid and up-to-date
- Study devices and study supplies are stored and accounted correctly
- etc.

The investigator must provide to the Sponsor and/or representative the necessary study records for a thorough review of the study's progress.

At monitoring visits radiographs, CRFs, photographs, casts and other study documents might be collected.

#### 13.2.5 Close out Visit

All routine monitoring functions must be completed prior to the study termination visit. During this last scheduled visit the monitor will also focus on the responsibilities of the investigator after the study is closed. The site should have answered any open query before the monitor schedules this visit, and the database (if not already closed) should be cleaned and locked. The monitor has to follow-up the finalization of all study logs and has to prepare copies of all documents necessary for the TMF as well as final check the IF for completeness. The monitor should prepare the IF and CRF in a matter that allows the investigator easy archiving.

### 13.2.6 Study Termination

The study can be discontinued early at the discretion of the principle investigator or the Sponsor in the case of any of the following:

- Occurrence of AEs unknown at the start of the study in with respect to their nature, severity, and duration, or the unexpected excessive incidence of known AEs
- New scientific knowledge obtained after the start of the study showing the ethical claim of the study is no longer valid

Version 6.0 Page 36 of 47

If the study or a study site is terminated before the aspired end of the study for any reason, the investigator should contact all active study subjects. Afterwards the investigator should apply the standard of care for implant therapy.

If the study is temporarily interrupted for any reason the subjects should be treated at the discretion of the investigator. Each investigator should take care that none of his subjects exceeds the absolute treatment time, unless it is medically indicated.

In terminating or temporarily interrupting situations, Straumann and the investigator will assure the adequate consideration is given to the protection of the subject's interests.

#### 13.2.7 Centre discontinuation

The study centre might be closed and the study terminated under the following circumstances:

- The centre is not recruiting a sufficient number of subjects or is unlikely to recruit a sufficient number of subjects
- The centre does not respond to study management requests
- Repeated protocol violations have been discovered

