### 4.4 Number of Subjects

This study will be performed in two clinical centres, one in Germany and one in Switzerland; these centres are expected to recruit 50 subjects in total, 25 subjects in test group, 25 subjects in control. Planned subject recruitment period is 3 months. The recruitment is competitive. Recruitment will be stopped as soon as recruitment is complete.

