#### 8.3 Subject Completion / Withdrawal

It is possible that a subject may withdraw from the study at any time without prejudice and will be offered an alternative treatment for his/her dental condition. Subjects will be advised of the need for the prescribed follow-up visits for their ongoing care, well-being, and collection of relevant study data. All subjects must agree to return to the clinic to complete these follow-up visits.

The investigator may withdraw any subject from the study in the case of:

- non-compliance with the protocol
- a serious adverse event or an adverse event, in the opinion of the investigator, which prevents the subject's further participation in the study.

If a subject is withdrawn from the study as outlined above, the subject must be followed for reporting of adverse events. Withdrawn subjects will be followed according to the standard of care at the study centre.

Version 6.0 Page 23 of 47

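### Closing a centre for slow recruitment can lose the primary endpoint of subjects already grafted there, and no adverse event reporting is stated after a termination

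*Combined protocol and SAP*

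**What the plan says.** - **Closure (13.2.7).** The section opens with "The study centre might be closed and the study terminated under the following circumstances". The first ground listed is "The centre is not recruiting a sufficient number of subjects or is unlikely to recruit a sufficient number of subjects".
- **What follows (13.2.6).** The rule covers single sites as well as the whole study: "If the study or a study site is terminated before the aspired end of the study for any reason", the investigator contacts the active subjects. Then: "Afterwards the investigator should apply the standard of care for implant therapy". No study visit, biopsy or adverse event (AE) reporting is mentioned after that point.
- **Safety trigger (13.2.6).** One ground for stopping the study early is new kinds of AE "or the unexpected excessive incidence of known AEs".
- **Individual withdrawal (8.3).** Here "the subject must be followed for reporting of adverse events", and the subject is also followed under the centre's standard of care.
- **Recruitment (4.4).** "Planned subject recruitment period is 3 months". "The recruitment is competitive", over two centres, with no number fixed per centre. Section 8.4 allows replacement of anyone lost from the per-protocol population while recruitment is still open.
- **Endpoint (10.2, 7.14, 7.15).** The primary endpoint is read from a core taken at visit 4, 6 months ± 7 days after the graft. The core comes from the centre of the implant osteotomy. The clinic's standard of care for implant placement begins only after it has been taken.

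**The concern.** Slow recruitment is a reason to stop randomising at a centre. It is not a reason to stop measuring subjects who have already been randomised and grafted. Sections 13.2.6 and 13.2.7 read together make no such distinction, so the plainest way to follow them is to hand grafted subjects back to routine care.

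The core is a research step that precedes standard-of-care implant placement, so a subject on standard of care alone has no instruction to give one. Once the implant is placed without a core, the ratio at that site cannot be recovered. The full analysis set (10.4.2) keeps subjects who terminate prematurely, but it cannot supply a ratio that was never measured.

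A second gap concerns safety data. After a termination, including one prompted by an excess of AEs, section 13.2.6 states less AE reporting than section 8.3 requires for one person who withdraws. The subjects already exposed are the ones whose reports would show the size of the problem in each arm.

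**Working it through.** **1. The plan's own sample size.** Inputs from 10.3: difference 0.4, common SD 0.5, two-sided α = 5%, power 80%, unpaired t-test.

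Normal approximation: n per group = 2 × (1.960 + 0.842)² × 0.5² / 0.4² = 2 × 7.85 × 1.5625 = 24.5, rounded up to 25. This reproduces the stated 25, and the other six entries of Table 1 reproduce in the same way. With the t distribution the answer at SD 0.5 is 26, and power at 25 per group is 79.1%. The plan needs 25 per group and randomises 25 per group (5.4), so no margin for losses is stated.

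**2. Timing.** The earliest visit 4 is 6 months minus 7 days = 6 − 7/30.44 = 5.77 months after the graft.

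- Closure at any time in the planned 3-month recruitment: 3 < 5.77, so none of that centre's subjects has reached visit 4.
- If recruitment overruns, some cores exist. Assume uniform accrual from the centre's first graft, still running at closure c months later. The fraction that has reached visit 4 is then (c − 5.77)/c:
  - c = 7: 1.23/7 = 18%
  - c = 9: 3.23/9 = 36%
  - c = 12: 6.23/12 = 52%

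**3. Power if endpoints are lost.** The documents give no number per centre, so the number lost is an assumption. Further assumptions are an even split over the arms and no replacement. The noncentrality parameter is (0.4/0.5) × √(n/2), with 2n − 2 degrees of freedom.

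| Lost of 50 | n per group | Noncentrality | Power |
|---|---|---|---|
| 0 | 25 | 2.83 | 79.1% |
| 4 | 23 | 2.71 | 75.6% |
| 10 | 20 | 2.53 | 69.3% |

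**4. AE reporting, section by section.**

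- 8.3 (one subject withdrawn): standard of care plus AE reporting.
- 13.2.6 (site or study terminated): standard of care; AE reporting not mentioned.
- 7.7: AEs are documented at study visits until the study ends, which gives no occasion for recording once visits stop.
- 9.13: AEs that arise in the course of the study are followed to resolution or steady state. It does not provide for capturing new events afterwards.

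**The case against.** Several points on the other side stand, and they limit the size of the problem.

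- **No order to discard.** A reader might infer that the protocol discards the primary endpoint of every subject randomised at a closed centre. It does not say so. Section 13.2.6 gives a care instruction; it neither forbids the biopsy nor orders data to be dropped. Closure under 13.2.7 is discretionary. All of a centre's subjects are exposed only if closure comes before about 5.8 months from its first graft, and the 3 months in 4.4 is only a plan.
- **Replacement.** While recruitment is open, 4.4 and 8.4 let the other centre make up the numbers. An early closure, which exposes the most subjects, is also the one most open to replacement. Replacement restores the count, but it does not justify losing outcomes from subjects already treated.
- **Few subjects.** A reader might carry the power table further: 20 lost (15 per group) would give 56.2%. Nothing in the documents supports that case. Twenty of 50 is close to an equal share of a two-centre trial, which hardly fits a centre closed for recruiting too few.
- **No contradiction with 8.3.** A reader might see 8.3 and 13.2.6 as conflicting. They deal with different events, and 8.3 itself combines standard of care with AE reporting, so that phrase alone does not end reporting. In addition, 13.2.6 asks for due regard to subjects' interests, and 12.1 asks the investigator to stay in contact and try to gather device safety information. These are general duties, though, and neither sets out AE reporting after a termination.

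**Conclusion.** The point holds as a defect of two stated rules. The number of outcomes at risk is unknown and possibly small. Following 13.2.6 after a recruitment closure under 13.2.7 can irrecoverably lose the 6-month endpoint of subjects already grafted at that centre. On the planned timeline no core would yet have been taken there.

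The illustrative cost is a fall in power from 79.1% to 75.6% with 4 lost, or to 69.3% with 10 lost. It rests on the plan's difference of 0.4 and SD of 0.5, an even split over arms, no replacement, and a number lost that the documents do not give.

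Separately, and whatever the timing, 13.2.6 states no AE reporting after a site or study termination, whereas 8.3 requires it after an individual withdrawal. That is a difference to be reconciled.

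**What to change.** - **13.2.7:** state that closure for insufficient recruitment stops new randomisation only. Subjects already grafted at that centre continue their scheduled study visits and data collection, including the visit 4 core with continued consent, and stay in the analysis.
- **13.2.6:** reconcile with 8.3, so that AE reporting continues for grafted subjects after an early site or study termination.

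The first change is confined to closure for recruitment. It does not ask for the core after a termination on safety or ethical grounds.

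The cost is about two sentences of text, plus monitoring at the closed centre for the rest of follow-up. For a subject grafted just before closure that is nominally 6 + 4 = 10 months, with visit 6 allowed 1 month either side.
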